- Develop strategies to encourage recruitment and address any issues with recruitment
- Be involved in the day-to-day running of the study by supporting the Chief Investigator
- Provide clinical or other expert guidance on clinical and practical queries and interpretation of data collected
- Provide responses to any issues or concerns raised by the chief investigator or the external ethics committees
- Input into the development of the statistical analysis plan
- Input into the interpretation and writing up of the study results

- Presentation of the study results at scientific meetings and in written publications

Schedule of meetings of the trial management group

The TMG will meet formally on a quarterly basis during the course of the study to monitor progress, completion of appropriate assessment and troubleshoot any issues raised during the study, either by participants or other members of the TMG. The agenda of these meetings and timetable will be driven by the chief investigator. It is anticipated the chief investigator will meet with individual members of the TMG more frequently as required. The patient representative will not be needed to attend all the TMG meetings, but will be invited to meet with the TMG on a six monthly basis to provide input on the progress of the study and future direction. The TMG meetings will be minuted and a record kept in the study file.

We will convene a Trial Steering Committee (TSC) who will meet formally in Year 1 and Year 2 of the study. Any significant concerns from the Trial Management Group will be escalated to the TSC. The TSC will receive the minutes from the TMG and a formal report of the progress of the study.

PROTOCOL CONTRIBUTORS

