2.1 Objectives

- To develop and adapt the READY for MS web-based Acceptance and Commitment Therapy programme for use in the UK.
- To assess the efficacy of using web-based ACT versus standard care in a randomised study.
- To use MS-PROACTIVE to provide the key underpinning data to support the delivery of a definite trial externally funded via the NIHR HTA programme.

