The adaptation phase will comprise an iterative process of user testing and content development to tailor 'READY for MS' to a UK workplace context. This will involve drawing on relevant principles of experience based co-design (Chisholm, Holtum & Springham, 2018) and digital user experience (UX) testing methodologies to assess user 'journeys' and relevance for self-guided therapeutic application in a range of UK workplace settings. READY for MS will be initially reviewed by the project team for its alignment with research objectives and outcomes, and any immediate changes made. 4 people PwMS (representative of genders, ages and educational level) will then be recruited to experientially review the digital program in terms of its suitability for a UK workplace context. The feedback of 2 employers will also be sought to enhance the co-design process. Participants' feedback will be considered by the research team and program modifications implemented accordingly for a final round of review. In particular, we will consider how the workbook, reflection exercises and directed home practice tasks can be tailored further to represent challenges typical to PwMS in UK workplaces. This process of user testing will also allow consideration of the form and nature of support provided by MS Specialist nurses to support therapeutic engagement.

There is a risk of a high rate of attrition with on-line psychological treatment. The MS Nurses will receive training in the READY programme and will provide planned telephone support at 2-3 weeks post-randomisation. Adherence and completion of the programme will be measured.

CONTROL: Standard care with a written information leaflet about employment and MS 'Work and MS:

IRAS 279736

An employee's guide' (MS Society, 2015).

PRIMARY OUTCOMES: MS Work Instability Scale (MS WIS) at 6 months after randomisation: 22-item, self-administered scale measuring work instability.

SECONDARY OUTCOMES: Health related quality of Life (EQ-5D, SF-12), mood (PHQ9), self-efficacy (Uni-dimensional Self efficacy Scale for Multiple Sclerosis - USE-MS), impact of MS, (Multiple Sclerosis Impact Scale-29, MSIS-29), fatigue (Neurological Fatigue Index for multiple sclerosis - NFI-MS), psychological flexibility (Comprehensive assessment of Acceptance and Commitment Therapy processes - CompPACT), participant satisfaction with the technology post-intervention (system usability scale - SUS).

PROCESS EVALUATION

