The process evaluation will comprise three phases.

3.1 Phase 1

In Phase I, academic and grey literature will be reviewed to identify stakeholders' theories concerning how ACT can be embedded into MS Specialist services and its impacts. In investigating the theoretical basis for work-focused ACT in this setting, we wish to understand the mechanism through which the intervention might be expected to 'work'. The precise search terms and inclusion and exclusion criteria for the literature review will be determined by the project team, in collaboration with subject-specialist librarians at the University of Leeds and Birkbeck University of London. We will conduct an exhaustive literature search of available health, psychology and social science databases that index research relevant to the topics above. The literature review will be used to inform the development of case studies in Phase 2 by reviewing the mechanisms by which READY for MS may work in this setting and the outcomes it may impact on. Specifically, it will inform development of the interview schedule and more broadly to situate the findings and conclusions of this study in the wider literature.

3.2 Phase 2

In Phase 2, a multi-site case study (n=4 in each site) to test and refine the candidate theories will be conducted. The case studies will include interviews with PwMS (pre-intervention/post-intervention/6 months follow up) and ACT facilitation staff (MS Specialist nurses). Participants/staff will be purposively sampled to provide maximum variation and information-rich cases (Patton, 1990; Mason, 2002).

3.3 Phase 3

In Phase III, 2 consensus workshops of 1 hour each will be conducted with 6-8 participants including PwMS and clinical staff to assess the extent to which the results of Phase II are generalisable and to refine the resulting theories to reflect the experience of a broader range of users and implementing health services.

Overall analysis: the analysis from phases 1 & 2 will be synthesised to determine what works for whom in what circumstances.

FOLLOW UP: Patient reported-outcome measures will be completed at baseline, 8 weeks and 6 months. Email/telephone reminders will be sent at each time point.

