6.1 Assessment and management of risk

PwMS who are excluded at screening due to having no work instability may feel disappointed at not being able to participate in the trial. We will explain that the main purpose of the trial is to find out if we can measure an effect on work instability and if they have no work instability to start with then no improvement in this can be measured.

There is a risk that completing the online sessions and workbook of READY for MS may highlight work related problems or other problems related to living with MS. The MS specialist nurses will provide both planned support and flexible support as required including signposting. Any significant issues involving psychological distress will be escalated according to the local pathways of care. This would include informing the GP and appropriate psychological support. READY for MS has been designed to improve resilience and the ability to cope with day to day life challenges. However, we acknowledge that there may be unintended consequences.

The benefit of participating in the study is that this research addresses one of the key priorities of the MS Society in improving self-management of MS. Although this study will not lead to any personal benefit it may lead to a larger trial and potentially an effective treatment in the future.

During the study the participant will be reminded of their right to withdraw from the study at any point, without the need to provide an explanation and the PIS will include the Project Manager's contact details for all queries throughout the duration of the study.

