6.4 Protocol compliance

The chief investigator will be responsible for all the recruitment, data collection and administration of assessments. The study participants will be informed about the protocol during the consent process and one of the consent criteria will be an agreement to adhere to the study protocol. The participants will be asked to make known any changes in their circumstances that might put them outside the eligibility criteria for the trial and they will be asked about this during every study visit. The chief investigator will log any protocol deviations and these will be made known to the TMG and where deemed appropriate, the chief investigator will also inform the local R&D team and REC.

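### The protocol concedes possible unintended consequences but plans no adverse-event or escalation recording in either arm, so harms beyond questionnaire scores cannot be compared by arm

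*Protocol*

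**What the plan says.** Section 6.1 identifies a programme-specific risk: "There is a risk that completing the online sessions and workbook of READY for MS may highlight work related problems", and the same sentence extends this to other difficulties of living with MS. It closes the topic with "However, we acknowledge that there may be unintended consequences". The stated response is nurse support, signposting and this: "Any significant issues involving psychological distress will be escalated according to the local pathways of care".

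Neither outcome list (section 2.2, and the primary and secondary outcomes in section 3) contains a harm event. Mood is a secondary outcome in both lists, as HADS in section 2.2 and as PHQ9 in section 3. The follow-up paragraph after section 3.3 says "Patient reported-outcome measures will be completed at baseline, 8 weeks and 6 months", with no restriction to one arm.

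The intervention text in section 3 says the MS nurses "will provide planned telephone support at 2-3 weeks post-randomisation". The control text describes standard care and a leaflet, with no matching call.

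On logging, section 6.4 says "The chief investigator will log any protocol deviations and these will be made known to the TMG". On oversight, the trial management text says "Any significant concerns from the Trial Management Group will be escalated to the TSC". Neither mentions adverse events. One objective in section 2.1 is "to provide the key underpinning data to support the delivery of a definite trial".

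**The concern.** The protocol foresees that the sessions could bring distressing problems to the surface, yet everything it sets up in response is care for the individual, not data. Nothing defines an adverse event, asks about one, counts escalations or reports either by arm. What is collected from participants has to be fixed in the protocol, because an analysis plan cannot recover events that were never recorded.

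What would reach the team informally would also be uneven. The one planned nurse call is part of programme support, so distress in the online arm has an extra route to notice. An informal tally would tend to make the programme look worse than control even if the true rates were equal.

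At stake is whether the definitive trial that this pilot is meant to inform can start with event-level harms data for both arms.

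**Working it through.** **1. Which harms the plan can and cannot see, by arm**

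| Type of harm | Seen in both arms as written? | Basis |
|---|---|---|
| Mood score worse at week 8 or month 6 | Yes | Secondary outcome, common schedule |
| Work instability or MS impact worse | Yes | MS-WIS and MSIS-29, same schedule |
| Distress episode that resolves between time points | No | Nothing is measured between week 8 and month 6 |
| Escalation to local pathways | No | Acted on, but no log is described |
| Serious event | No | No item and no log |
| Harm behind a withdrawal | No | Section 6.1 lets participants leave without giving a reason |

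The unmeasured stretch overlaps the programme. Section 3 gives 7 weekly modules and a booster five weeks after the last, so the booster falls at about week 7 + 5 = 12, after the week-8 questionnaire.

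**2. Inputs and the plan's own figures (section 5.2.1)**

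The sample is 88, randomised 1:1, so 88 / 2 = 44 per arm. The attrition rate used for planning is 20%.

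- Attrition margin: 1.96 × √(0.2 × 0.8 / 88) = 0.084, stated as ±8%. Reproduced.
- Participation margin: 1.96 × √(0.5 × 0.5 / 176) = 0.074, stated as ±7%. Reproduced.
- Retained: 88 × 0.8 = 70.4, consistent with the stated minimum of 70 and giving about 35 per arm.

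**3. What the mood scale can already show**

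With 35 per arm, the 95% half-width for a standardised difference is 1.96 × √(2/35) = 0.47 SD. The difference detectable with 80% power is (1.96 + 0.842) × √(2/35) = 0.67 SD. With 44 per arm these are 0.42 and 0.60 SD. An arm comparison of mood scores is therefore possible, though imprecise.

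**4. What systematic event recording would add**

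The protocol gives no harm rate, so every rate here is an assumption. The chance of at least one event in an arm of n is 1 − (1 − p)^n:

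| Assumed p | n = 44 | n = 35 |
|---|---|---|
| 2% | 1 − 0.98^44 = 58.9% | 1 − 0.98^35 = 50.7% |
| 5% | 1 − 0.95^44 = 89.5% | 1 − 0.95^35 = 83.4% |
| 10% | 1 − 0.90^44 = 99.0% | 1 − 0.90^35 = 97.5% |

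If no events occur, the one-sided 95% upper limit is 1 − 0.05^(1/n): 6.6% for n = 44 and 8.2% for n = 35.

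**5. What it would not add**

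For an assumed 5% against 15%, power uses the normal approximation with pooled variance under the null.

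- n = 44: (0.10 − 1.96 × √(2 × 0.1 × 0.9 / 44)) / √((0.05 × 0.95 + 0.15 × 0.85) / 44) = −0.40, so power is 34%.
- n = 35: the same formula gives −0.57, so power is 28%.

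The 95% half-width for that difference is ±12 points with 44 per arm and ±14 points with 35. The result would be descriptive.

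**The case against.** The strongest reply is that the harms the protocol names are already measured. Mood, work instability and MS impact are collected on one schedule with no restriction by arm, each scale can show worsening as well as benefit, and a table of worsening against a threshold is ordinarily left to the analysis plan. The questionnaires also carry none of the asymmetry of the nurse call. All of this stands. A reader might infer that the pilot could not say at all whether distress is more common with the programme, or that no data on distress would exist. The documents do not support either reading.

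A reader might also infer that the protocol regards the programme as harmful. It does not: it says problems may be highlighted and allows for unintended consequences.

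Other routes exist. Interviews are planned at three stages, and significant concerns go to the Trial Steering Committee. But the interviews cover only four people per site and are timed around doing the course, and no harms count is described as feeding the committee. Neither route gives a comparison by arm.

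Finally, absence is judged on the text available, from which some front pages have been removed.

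What the objection leaves untouched is event-type harm: episodes between questionnaires, escalations, serious events and the reasons behind withdrawal.

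**Conclusion.** The concern holds in a limited form. The protocol anticipates unintended consequences but plans no recording of adverse events or escalations in either arm. Distress can be compared by arm only as questionnaire scores, to about ±0.47 SD with 35 per arm, and the two names given for the mood scale must first be reconciled. Event-type harms cannot be compared, and incidental reports would lean towards the online arm.

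Recording in both arms would, at an assumed 5% rate, have about a 90% chance of showing at least one event in an arm of 44 (83% with 35). Zero events would bound the rate below 6.6% (8.2% with 35). These figures assume independent events and full ascertainment among those who respond. They support a descriptive harms table, not a powered comparison. This is an inexpensive improvement; it does not undermine the primary analysis.

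**What to change.** - Add a short fixed harms question (new or worse distress, any serious event) to the week-8 and month-6 questionnaires, worded identically for both arms and covering the time since the previous questionnaire.
- Keep a log of escalations by arm. Note how each came to light (planned call, usual care, other), because the log alone would still reflect the extra contact in the online arm.
- Send a descriptive table by arm to the existing Trial Steering Committee, which meets in each of the two years.
- Reconcile HADS and PHQ9 so that it is clear which mood scale is collected.

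How any individual is managed stays with the existing local pathways.

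The cost is two or three items, a simple log and one table, with no extra visits. The downside is a slightly longer questionnaire. The items will still miss participants who withdraw and return no questionnaire; the log would recover only those whose distress was escalated.

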6.2 Research Ethics Committee (REC) and other Regulatory review & reports

Prior to the start of the study a favourable opinion will be sought from the Leeds Teaching Hospitals Trust research ethics committee (REC) and research and development (R&D) department, to ensure the protocol complies with local regulations. The study has also been submitted via the portfolio application form for consideration of support by the National Institute for Health Research Clinical Support Network in England. The study will also be submitted to the Health Research Authority (HRA) via the Integrated Research Application System (IRAS). Subsequently, any substantial amendments that require review by the HRA will then be applied for separately and the Leeds Teaching Hospitals Trust REC will be notified of any amendments to the protocol. Where required the chief investigator will produce an annual report to the Leeds Teaching Hospitals Trust REC. The chief investigator will notify the Leeds Teaching Hospitals Trust REC and NHS HRA upon completion of the study. Within one year after the end of the study or if otherwise specified, the chief investigator will submit a final report with the results to the HRA and Leeds Teaching Hospitals REC.

6.2.1 Regulatory Review & Compliance

Before any patients are recruited into the study, the chief investigator will ensure that appropriate approvals from the local REC and R&D department are in place. The study will also need to have received HRA approval via IRAS. Any subsequent amendments to the protocol will be submitted via IRAS for HRA approval prior to any change in the study parameters. The chief investigator will work with the R&D department at the study site as well as the TMG so they can put the necessary arrangements in place to implement the amendment, to confirm their support for the study as amended. As part of the required clinical standard in conducting research within the NHS, the chief investigator has Good Clinical Practice (GCP) certification.

6.2.2 Amendments

The chief investigator will be responsible for the decision to make any amendments to the protocol after agreement with the co-investigators. For any substantial amendment to the protocol, the chief investigator will submit a valid notice of amendment to the HRA for consideration via IRAS. Amendments will also be notified to the

local Leeds R&D team to assess whether the amendment affects the NHS permission for that site. The protocol version with the amendment will be updated and the most recent version of the protocol will be disseminated to all relevant study personnel. The updated version of the protocol as well as the historical version of the protocol will be filed in the site file.

6.3 Patient & Public Involvement

People with MS (PwMS) have brought their lived experience into the design of MS-PROACTIVE.

Design:

We worked closely with PwMS in the co-development of the MS-Work Instability Scale. This is the primary outcome measure in the MS-PROACTIVE trial.

The 'READY for MS' Acceptance and Commitment Therapy programme was developed by [name] in Australia to improve resilience and self-efficacy. The programme has been tested by PwMS in Australia and in Italy. Our PwMS advisors favour an intervention to improve self-efficacy that is convenient and empowers them to take control and manage their own situation. PwMS consistently reported they wanted to be more informed and involved with their own care and that MS-PROACTIVE offers opportunities for better health through supported self-care.

We have been working with Shift.ms, the social network for PwMS, who have helped us design the research. Shift.ms were keen for us to use a web-based type of therapy that would be flexible and easy for people who are working to use in their own time.

We submitted the initial plan for this study to the MS Society's Lay Research Network for review and advice on the application development. We received five detailed reviews from Research Network members on developing the project plan. Based on the reviews we have changed the proposal by adjusting the time frame

IRAS 279736

of the questionnaires, providing more detail on the content and length of sessions and included planned MS Nurse support in addition to the usual flexible support provided.

Four PwMS have provided verbal and written feedback on the Participant Information Sheet. This feedback has been incorporated in the current version.

Management of the research:

The Chief Executive of Shift.ms who has multiple sclerosis is a Co-Investigator for this project and a member of the Trial Management Group. The Trial Steering Committee will have representation from PwMS.

Undertaking the research:

In the first phase of the project four PwMS will be asked to consent to an external feasibility phase of the study. These four participants will trial the online version of READY for MS and advise on any modifications required and their experience of completing the online sessions. They will also advise on any changes required to the workbook. Data from these four participants will not contribute to the main pilot study analysis.

In the pilot study 88 PwMS will be randomised to either completing the online READY for MS sessions and standard care or standard care.

4 of the participants at each site will be asked to consent to be interviewed before doing the course, after completing the course and 6 months later. This is part of the process evaluation to work out how READY for MS works in practice.

Dissemination:

Shift.ms will support co-production of a plain English end of trial paper for trial participants, their families and the wider MS community especially PwMS and their employers.

6.4 Protocol compliance

The chief investigator will be responsible for all the recruitment, data collection and administration of assessments. The study participants will be informed about the protocol during the consent process and one of the consent criteria will be an agreement to adhere to the study protocol. The participants will be asked to make known any changes in their circumstances that might put them outside the eligibility criteria for the trial and they will be asked about this during every study visit. The chief investigator will log any protocol deviations and these will be made known to the TMG and where deemed appropriate, the chief investigator will also inform the local R&D team and REC.

